**FORM: Application for Human Research**

| NUMBER | FORM DATE | PAGE |
|--------|-----------|----------|
| F200 | 02/2014 | 14 of 44 |

360 function, alterations in proton metabolites in the limbic system and medial prefrontal cortex, and reduced
361 PTSD symptom severity at follow-up assessment. The following are the Specific Aims and Hypotheses:

362 **AIM 1:** Evidence suggests that morning bright light therapy suppresses daytime melatonin and
363 leads to an entrainment of the circadian rhythm that modulates daytime alertness and nighttime sleep.
364 The first objective will be to assess the validity of this effect in PTSD patients.

365 **Hypothesis 1: Six weeks of BLT will improve sleep relative to PL among PTSD subjects.**

366 **1a:** Six weeks of morning blue light therapy (BLT) will improve objective and subjective
367 measures of sleep duration and quality as measured by actigraphy, sleep logs, sleep scales, and
368 polysomnography relative to an amber light placebo therapy (PL) condition.

369 **AIM 2:** If light therapy is successful in entraining the circadian rhythm and improving nighttime
370 sleep in patients with PTSD, this should be associated with improvement in symptoms and cognitive
371 functioning, as sleep has been shown to be critical in the process of extinguishing conditioned fears.
372 Therefore, the second Aim is to evaluate the association between changes in sleep patterns and
373 improvement in symptom expression, emotional wellbeing, and cognitive functioning in patients with
374 PTSD. However, even if Aim 1 is not successful, the present study will provide important cross-sectional
375 data regarding the relationship between measured sleep, cognitive functioning, and fear extinction in
376 individuals with PTSD.

377 **Hypothesis 2: BL will improve cognitive functioning, symptoms of PTSD, and generalization of**
378 **fear extinction relative to PL.**

379 **2a:** Six weeks of BL will improve measures of neurocognitive (i.e., memory and executive
380 functions) and mood functioning relative to PL.

381 **2b:** The PTSD group receiving six weeks of BL will show significant reduction in self-
382 reported symptom scores on the PTSD symptom checklist and CAPS, lower emotional distress on clinical
383 measures, and greater *generalization of conditioned fear extinction* relative to the PTSD group receiving
384 PL.

385 **AIM 3:** At present, there are no known studies that have examined the neurobiological correlates
386 of symptom improvement in patients with PTSD following light exposure therapy. The present study
387 aims to provide clear evidence of functional and neurochemical changes that are associated with changes
388 in sleep, cognition, and PTSD symptoms from pre- to post-treatment. Even if Aim 1 is not supported, the
389 obtained cross sectional data will provide critical insights regarding the association between sleep,
390 neurometabolites, and brain function within patients with PTSD. This correlational information is
391 currently lacking for PTSD and will fill an important knowledge gap regardless of whether the light
392 therapy is successful.

393 **Hypothesis 3: Six weeks of BL will produce reliable changes in brain activation and**
394 **neurochemistry relative to PL, particularly for PTSD subjects.**

395 **3a:** Relative to PL, six weeks of BL will lead to significantly increased ventromedial
396 prefrontal activation and reduced amygdala activation during the backward masked affect fMRI task.

397 **3b:** Relative to PL, six weeks of BL will lead to significantly greater negative functional
398 connectivity between the ventromedial prefrontal cortex and amygdala during resting state fMRI.

399 **3c:** Relative to PL, six weeks of BL will be associated with increased activation of the
400 VMPFC, and reduced activation within the amygdala and dorso-medial prefrontal cortex during the
401 extinction recall scan.

**FORM: Application for Human Research**

| NUMBER | FORM DATE | PAGE |
|--------|-----------|----------|
| F200 | 02/2014 | 15 of 44 |

402 **3d:** Relative to PL, six weeks of BL will be associated with increased levels of GABA and
403 reduced glutamate in the amygdala-hippocampal complex and anterior cingulate gyrus as measured by
404 proton magnetic resonance spectroscopy (1H MRS).

405 **3e:** Relative to PL, six weeks of BL will produce increased levels of N-acetyl-aspartate
406 (NAA), choline (Cho), and reduced phosphocreatine (Cr) within the amygdala-hippocampal complex and
407 anterior cingulate gyrus.

408 **AIM 4:** The fourth Aim is to demonstrate whether changes in subjective and objective measures
409 of sleep are associated with changes in symptom severity, cognitive functioning, brain activation, and
410 neurochemistry. Regardless of the success of the light therapy approach outcome in Aim 1, the available
411 data will provide some of the first longitudinal data examining changes in sleep patterns over time in
412 individuals with PTSD and their correlation with these other metrics. Thus, useful data will be acquired
413 even if the primary hypothesis of Aim 1 is not supported.

414 **Hypothesis 4: Improvements in sleep noted in Hypothesis 1, will be linearly correlated with
415 improvements in cognitive and symptom functioning in Hypothesis 2 and structural and functional
416 brain changes in Hypothesis 3.**

417 **4a:** Changes in sleep parameters identified in Hypothesis 1 will correlate with
418 improvements in memory, executive functioning, and neuropsychological performance on neurocognitive
419 measures described in Hypothesis 2.

420 **4b:** Changes in sleep parameters identified in Hypothesis 1 will correlate with changes in
421 neurochemistry as outlined in Hypothesis 3d and 3e above.

423 **2) Lay Summary (approximately 400 words)**

424 Sleep disturbance is nearly ubiquitous among individuals suffering from PTSD and is a major problem
425 among service members returning from combat deployments. Recent evidence suggests that adequate
426 restorative sleep may a crucial component in the ability to generalize fear extinction learning, and
427 ultimately may be a key feature in the process of recovery from PTSD. The proposed study aims to test a
428 novel, inexpensive, and easy to use non-pharmacologic approach to improving sleep among service
429 members and other individuals with PTSD. Our approach is based on recent scientific discoveries
430 regarding the role of the photosensitive retinal ganglion cell system in regulating sleep-wake patterns.
431 Moreover, our protocol employs a novel, non-pharmacologic intervention for influencing this system to
432 regulate sleep and cognition. Primary outcome measures will include not only PTSD symptom
433 improvement but also include cutting-edge neuroimaging of brain structure, function, connectivity, and
434 neurochemistry changes. The proposal is firmly **grounded in the emerging scientific literature**
435 regarding sleep, light exposure, brain function, anxiety, and resilience. Prior evidence suggests that blue
436 light therapy is effective for improving mood and fatigue, and our pilot data further suggest that this
437 treatment may be effective for improving daytime sleepiness and brain functioning in brain injured
438 individuals. Thus, this intervention, in our own research and in the work of others, has been shown to
439 affect critical sleep regulatory systems. Improving sleep may be a vital component of recovery in these
440 service members. Our approach would directly address this issue. Our preliminary data have shown that
441 this approach is extremely well tolerated and is effective for improving sleep, mood, cognitive
442 performance, and brain function among individuals with brain injuries. The protocol is actually less

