**FORM: Application for Human Research**

| NUMBER | FORM DATE | PAGE |
|--------|-----------|---------|
| F200 | 02/2014 | 5 of 44 |

7. The Principal Investigator hereby affirms that ALL individuals who meet the definition of "investigator" for this project in the current "Policy on Investigator Conflict of Interest in Research" have completed the mandatory Conflict of Interest training Yes (<http://orcr.arizona.edu/coi/training>) and Disclosure of Significant Financial Interests (<https://uavpr.arizona.edu/COI/>).

8. Will this project be registered on ClinicalTrials.gov because ...? Yes No

- the local PI is the sponsor of the clinical trial (including NIH-funded clinical trials where the local PI is the funding recipient OR IND holder);
OR
- The PI has been designated by a sponsor, contractor, grantee, or awardee to register the clinical trial to [ClinicalTrials.gov](#), as the [Responsible Party](#) (responsible for conducting the trial, and has sufficient data rights)

If yes, please check the appropriate box:

[ClinicalTrials.gov](#) "NCT" number for this trial (define): NCT02370173
 Registration pending
 Clinical trial does not require registration (click above to see what studies qualify)

40

SECTION 3. PROJECT NARRATIVE

41

1) Background

42 During the past decade, over 2 million U.S. military personnel have deployed on potentially dangerous
43 missions in support of the wars in Iraq and Afghanistan [1]. Combat duty is inherently hazardous and
44 many deployed Soldiers have experienced intense and personally life-threatening situations or witnessed
45 horrific and traumatic events. The neuroendocrine stress response that is associated with these types of
46 potentially life-threatening experiences prepares the brain and body for survival. As part of this survival
47 response, several brain systems become hyper-responsive and sensitized to potential threat. In particular,
48 exaggerated amygdala responses during stressful experiences enhance the encoding of vivid and indelible
49 emotional memories [2, 3]. For some combat veterans, the intensity and horrific nature of these
50 experiences is perceived as so overwhelming that they continue to have sustained physiological arousal,
51 heightened startle reflexes, and uncontrollable intrusive memories and nightmares that persist for years or
52 even decades after the traumatic experience. If these symptoms are sustained and lead to impairments in

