 211 emotional dysregulation model [83-92]. Notably, the anterior cingulate cortex (ACC) and hippocampus
 212 demonstrate abnormalities in neurometabolites such as n-acetylaspartate (NAA), a putative marker of
 213 neuronal integrity, in patients with PTSD (Karl and Werner, 2010).[83-92] Because sleep disruption is
 214 one of the most common symptoms of PTSD, the associated reduction in sleep quantity and quality may
 215 serve to exacerbate the difficulties these patients have regulating emotions, serving to develop a vicious
 216 circle of hyperarousal, decreased sleep, and emotional dysregulation.

[figure not shown]

Figure 2. Masked Affect Task: Preliminary fMRI data from various anxiety disorders (n = 65) shows greater amygdala activation and reduced VMPFC activation. Note that amygdala activation is greatest among PTSD subjects (n = 14) relative to small animal phobias (n = 15), par

[figure not shown]

Figure 3. Scores on the Pittsburgh Sleep Quality Index (PSQI) showed greater reduction in sleep problems following 6-weeks of treatment with the active blue light (n = 7) treatment versus amber light (n = 5) placebo.

FORM: Application for Human Research
NUMBER

F200

FORM DATE

02/2014

PAGE

[figure not shown]
10 of 44

217 The proposed investigation will examine changes in sleepiness, neuropsychological functioning,
 218 symptom severity, as well as brain functioning and neurochemistry before and after a 6-week treatment
 219 period with BLT. To this end, we have collected pilot data showing that 6-weeks of daily morning
 220 exposure to BL improves sleep, cognitive performance, brain functioning, and underlying axonal integrity
 221 in concussion patients compared to equivalent exposure to amber placebo light (PL). Our preliminary
 222 findings in a small pilot sample of 12 participants (BL $n = 7$; PL $n = 5$) suggest that BL treatment may be
 223 effective at improving sleep and accelerating recovery. While fully cognizant of the fact that these data
 224 are preliminary, we present the following findings to provide support for the feasibility of the study
 225 design and demonstrate our capacity to collect, process, and analyze relevant data.

226 Subjective Symptom Improvement. Figure 3 depicts subjective sleep quality, as measured with
 227 the Pittsburgh Sleep Quality Index (PSQI) pre- and post-
 228 intervention by group. While there was no change in the Amber
 229 Light Placebo group between pre- and post-treatment assessment,

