781 will complete a comprehensive baseline assessment of neurocognitive and emotional functioning, coping
782 capacity, and resilience. Participants will also undergo a validated *de novo* fear conditioning and
783 extinction procedure [98-101], and a series of functional neuroimaging and neurochemistry scans.
784 Additionally, participants will complete subjective and objective measures of sleepiness and alertness
785 throughout the day. The following specific tasks and procedures will be administered during the
786 assessment session:

787 **Emotional Functioning/Coping/Symptom Severity:** PTSD severity will be assessed using the
788 20-item National Center for PTSD Checklist, Military Version (PCL-5), Patient Health Questionnaire
789 (PHQ-9), and Clinician Administered PTSD Scale-5 (CAPS-5). Further assessment of psychopathology
790 will be made via administration of the Beck Depression Inventory (BDI-II); Beck Anxiety Inventory
791 (BAI); and Spielberger State-Trait Anxiety Inventory (STA). Participants will also complete measures
792 of resilience (Connor-Davidson Resilience Scale (CD-RISC)), Evaluation of Risks (EVAR), the Satisfaction
793 with Life Scale (SWLS) and the Gratitude Questionnaire (GQ6). The Balloon Analogue Risk Test
794 (BART) will be done to measure risk taking.

795 **Subjective Sleep Measures:** To assess general sleep quality, daytime sleepiness, and
796 parasomnias, participants will complete the Pittsburgh Sleep Quality Index (PSQI)[102], the Epworth
797 Sleepiness Scale (ESS) [103], the Insomnia Severity Index (ISI)[104], and the Disturbing Dream and
798 Nightmare Severity Index (DDNSI) [22]. The Stanford Sleepiness Scale (SSS) [105] will be completed at

FORM: Application for Human Research

[figure not shown]
| NUMBER | FORM DATE | PAGE |
|--------|-----------|----------|
| F200 | 02/2014 | 25 of 44 |

799 three times during the assessment day. The Functional Outcome of Sleep Questionnaire (FOSQ) and
 800 Sleep Diaries A & B will also be done.

801 **Neurocognitive Assessment:** All participants will complete a comprehensive neurocognitive
 802 assessment battery to include:

803 1. Repeatable Battery for the Assessment of Neuropsychological Status (RBANS). The
 804 RBANS is a brief battery of well-normed neuropsychological tests with two alternate forms (RBANS A
 805 and RBANS B) to permit repeated testing. The test provides several index scores, including: Total Score,

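### The sleep–symptom correlation in Aim 4 and Hypothesis 4 is partly circular for the subjective sleep measures, because no PTSD score without sleep and nightmare items is planned

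*Combined protocol and SAP*

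**What the plan says.** All references are to the combined protocol and SAP.

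- **Sleep as a PTSD symptom.** Section A.3 (Preliminary Data) calls sleep disruption "one of the most common symptoms of PTSD, the associated reduction in sleep quantity and quality may" worsen emotion regulation. The Background makes the same point in its discussion of sleep disruption. Its opening paragraph includes "heightened startle reflexes, and uncontrollable intrusive memories and nightmares that persist for years or" decades among the complaints that, if sustained and impairing, may lead to a PTSD diagnosis.
- **PTSD severity scales.** Section 7, under emotional functioning and symptom severity, names the "20-item National Center for PTSD Checklist, Military Version (PCL-5), Patient Health Questionnaire" (PHQ-9) and the CAPS-5. It gives no item content beyond the count of 20 for the PCL-5.
- **Sleep measures.** Hypothesis 1a uses actigraphy, sleep logs, sleep scales and polysomnography. The subjective scales in Section 7 include the PSQI, the ISI and the DDNSI, which is a nightmare index.
- **The link to be tested.** Aim 4 asks whether changes in subjective and objective measures "of sleep are associated with changes in symptom severity, cognitive functioning, brain activation, and" neurochemistry. The Hypothesis 4 statement begins "Improvements in sleep noted in Hypothesis 1, will be linearly correlated with" and continues with "improvements in cognitive and symptom functioning in Hypothesis 2 and structural and functional" brain changes. Its two numbered parts are 4a (neurocognitive performance) and 4b (neurochemistry).
- **The treatment comparison.** Hypothesis 2b predicts a reduction in self-"reported symptom scores on the PTSD symptom checklist and CAPS, lower emotional distress on clinical" measures, and greater generalization of fear extinction. The Lay Summary says: "Primary outcome measures will include not only PTSD symptom" improvement.
- **Analysis.** Section D plans ANOVAs or mixed models on symptom scores, then correlation and linear regression of change indices on sleep variables. It defines no PTSD score without sleep content and no sensitivity analysis for the overlap.

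**The concern.** The trial tests a sleep intervention and proposes that better sleep reduces PTSD. If the symptom score counts sleep disturbance and nightmares, part of its change is sleep change. Correlating that score with a sleep or nightmare scale then correlates a complaint partly with itself.

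The quantity of interest is whether improved sleep goes with improvement in the other PTSD symptoms: re-experiencing apart from nightmares, avoidance, mood, and arousal apart from sleep. The planned correlation mixes that with item overlap. A modest positive result could not be read as evidence for the mechanism.

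**Working it through.** **1. The plan's own figure.** The Power Analysis gives power of 0.84 for r = .30 with N = 90, two-sided α = .05. A noncentral t with 88 df and noncentrality r/√(1−r²)·√N gives 0.839, so the figure reproduces. Fisher's z gives 0.823. The smallest correlation that reaches significance is .207. The overlap does not make the power figure wrong; it changes what a significant result means.

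**2. Inputs that are assumptions (not in the documents).**
- k of the 20 items concern sleep or nightmares: k = 1, 2 or 3.
- Item change scores have equal (unit) variance.
- The sleep items' changes correlate .4 with each other.
- The other items' changes correlate ρ with each other (0 to .5) and are unrelated to sleep. This is the case in which the hypothesis about other symptoms is false.
- The outside sleep measure's change correlates r_s with each sleep item (.3 to .7).

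**3. Formula.** The correlation of the full score with the sleep measure, through overlap alone, is

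r = k·r_s / √[ k + 0.4k(k−1) + (20−k) + (20−k)(19−k)ρ ].

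For k = 2 the quantity under the root is 2.8 + 18 + 306ρ.

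**4. Results for k = 2, N = 90, two-sided 5% test.**

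| ρ | r_s | r | P(significant) |
|---|---|---|---|
| 0 | .7 | 1.4/√20.8 = .307 | 86% |
| .1 | .3 | 0.6/√51.4 = .084 | 12% |
| .1 | .5 | 1.0/√51.4 = .139 | 26% |
| .1 | .7 | 1.4/√51.4 = .195 | 46% |
| .3 | .5 | 1.0/√112.6 = .094 | 14% |
| .5 | .3 | 0.6/√173.8 = .046 | 7% |
| .5 | .7 | 1.4/√173.8 = .106 | 17% |

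The row with ρ = 0 is a limiting case, since items of one severity scale would be expected to change together. For ρ of .1 to .5 the rejection rate runs from 7% to 46%.

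**5. Other item counts (ρ from 0 to .5, r_s from .3 to .7).** With one item, r runs from 0.3/√191 = .02 to 0.7/√20 = .16. With three items it runs from 0.9/√158.4 = .07 to 2.1/√22.4 = .44.

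**6. Weaker tracking of the items.** If the sleep measure tracks one item at .5 and the other at .2 (k = 2, ρ = .1 to .5), r is 0.7/√51.4 = .098 down to 0.7/√173.8 = .053, with rejection in 15% to 8% of trials. If it tracks both at .2, which might describe actigraphy, r is .056 to .030 and rejection 8% to 6%.

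**7. Hypothesis 2b.** Suppose treatment shifts each of two sleep items by 0.5 to 1.0 SD of change and nothing else. The standardized difference on the full score is 2 × shift / √(2.8 + 18 + 306ρ). For ρ of .1 to .5 this is 1.0/√173.8 = 0.08 up to 2.0/√51.4 = 0.28. With 45 per group, a two-sided 5% t-test is significant in 6.5% to 26% of trials.

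**8. With the sleep items removed.** Under the same assumptions r = 0 and d = 0, and both tests reject at 5%. Power at a true r of .30 with N = 90 stays at 0.84.

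**The case against.** **The item content is not printed.** This stands. That the scales contain sleep and nightmare items is inferred from the protocol's account of PTSD symptoms and its use of these scales for PTSD severity. The number of items is assumed, which is why a range is shown. A reader might extend the point to the PHQ-9 and BDI-II. The documents give neither those scales' items nor any statement about their content that would support this, so it is not claimed.

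**Not all of Hypothesis 4 is exposed.** This also stands. Hypotheses 4a and 4b use no PTSD scale. Only Aim 4's symptom clause and the symptom clause of the Hypothesis 4 statement are affected.

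**The trial has other evidence.** A reader might infer that the plan cannot tell a sleep-only effect from a wider one. That goes too far. Fear extinction is measured by skin conductance, Hypotheses 3a to 3c use imaging, and sleep is also measured by actigraphy and polysomnography. None of these shares questionnaire items with the PTSD scales. They do not repair the correlation with the subjective scales, however, and Aim 4 includes those explicitly.

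**Better sleep is genuine improvement in one PTSD symptom.** This is right for Hypothesis 2b, and the full score should stay as its main analysis. A reader might also infer that a light improving only sleep would make 2b positive. On the figures in step 7, roughly three quarters or more of such trials would not be significant.

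**The upper end of the range is generous.** This is fair. At r_s = .7 for both items, two item changes would explain 2 × .49/1.4 = 70% of the sleep scale's change. The lower half of the range is more plausible for most measures.

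**Conclusion.** The concern holds for the symptom part of Aim 4 and Hypothesis 4 when sleep is measured by self-report, including the nightmare index. Partly circular is the right strength. The spurious correlation is often modest, about .05 to .20 with two overlapping items and ρ of .1 to .5. It can still be a material share of the r = .30 for which the plan is powered, and it raises a nominal 5% test to about 7% to 46%. These sizes rest on assumed item counts and correlations, and on the scenario that other PTSD symptoms are unrelated to sleep.

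For Hypothesis 2b the issue is one of interpretation: a gain carried by sleep items should not by itself be described as global PTSD improvement. No figure stated in the plan is wrong on this account.

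**What to change.** 1. For the symptom part of Aim 4 and Hypothesis 4, pre-specify PCL-5 and CAPS-5 scores that leave out every sleep-disturbance and nightmare item, and list the excluded items. Base any conclusion that sleep improvement relates to improvement in other PTSD symptoms on these reduced scores.
2. Report the same correlations with the actigraphy and polysomnography measures alongside those with the subjective scales. Dropping items does not remove the shared self-report method.
3. For Hypothesis 2b, keep the full scores as the main analysis. Add the reduced scores as a sensitivity analysis, to be consulted before claiming global PTSD improvement.
4. State that item-level responses will be kept. The documents describe administering the scales and entering data in REDCap, but do not say this.

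The cost is a few lines of analysis text and a non-standard score reported beside the standard one. No extra participants, visits or instruments are needed. The choice should be fixed before outcome data are examined.
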